5.4 Biomarker analysis

The subject's consent to the use of donated biological samples (i.e. blood, sputum, endobronchial biopsies and bone marrow aspirates) is mandatory.

5.4.1 Storage, re-use and destruction of biological samples

Samples may be stored for a maximum of 15 years from the date of the Last Subject's Last Visit, after which they will be destroyed. If a subject withdraws consent to allow samples for future use they may continue with their samples being used for the main study. The results of this biomarker research will be reported either in the Clinical Study Report itself or as an addendum, or separately in a scientific report or publication. The results of this biomarker research may be pooled with biomarker data from other studies with the study drug to generate hypotheses to be tested in future research. Any residual samples may be used for future biomarker research.

5.4.2 Labelling and shipment of biological samples

The Principal Investigator ensures that samples are labelled and shipped in accordance with the Laboratory Manual and the Biological Substance, Category B Regulations (materials containing or suspected to contain infectious substances that do not meet Category A criteria), see [Appendix B](#) 'IATA 6.2 Guidance Document'.

Any samples identified as Infectious Category A materials are not shipped and no further samples will be taken from the subject unless agreed with AstraZeneca and appropriate labelling, shipment and containment provisions are approved.

5.4.3 Chain of custody of biological samples

A full chain of custody is maintained for all samples throughout their lifecycle.

The Principal Investigator keeps full traceability of all collected samples from subjects (including blood, sputum, bronchial biopsies and bone marrow aspirates) during storage at the centre until shipment or disposal (where appropriate) and keeps documentation of all shipments.

The sample receiver keeps full traceability of the samples while in storage and during use until used/disposed of or until further shipment and keeps documentation of receipt of arrival.

AstraZeneca keeps oversight of the entire life cycle through internal procedures, monitoring of study sites and auditing of external laboratory providers.

Samples retained for further use are registered in the AstraZeneca Biobank during the entire life cycle.

5.4.4 Withdrawal of Informed Consent for donated biological samples

If a subject withdraws consent to the use of donated biological samples, the samples will be disposed of/destroyed, and the action documented. If samples are already analysed, AstraZeneca is not obliged to destroy the results of this research.

The Principal Investigator:

- Ensures subjects' withdrawal of informed consent to the use of donated samples is notified immediately to AstraZeneca
- Ensures that biological samples from that subject, if stored at the study site, are immediately identified, disposed of /destroyed, and the action documented
- Ensures the laboratory(ies) holding the samples is/are informed about the withdrawn consent immediately and that samples are disposed of/destroyed, the action documented and the signed document returned to the study site
- Ensures that the subject and AstraZeneca are informed about the sample disposal.

AstraZeneca ensures the central laboratory(ies) holding the samples is/are informed about the withdrawn consent immediately and that samples are disposed of/destroyed and the action documented and returned to the study site.

6. SAFETY REPORTING AND MEDICAL MANAGEMENT

The Principal Investigator is responsible for ensuring that all staff involved in the study are familiar with the content of this section.

6.1 Definition of adverse events

An adverse event (AE) is the development of an undesirable medical condition or the deterioration of a pre-existing medical condition following or during exposure to a pharmaceutical product, whether or not considered causally related to the product. An undesirable medical condition can be symptoms (e.g., nausea, chest pain), signs (e.g., tachycardia, enlarged liver) or the abnormal results of an investigation (e.g., laboratory findings, electrocardiogram). In clinical studies, an AE can include an undesirable medical condition occurring at any time, including run-in or washout periods, even if no study treatment has been administered.

The term AE is used to include both serious and non-serious AEs.

6.2 Definitions of serious adverse event

A serious adverse event (SAE) is an AE occurring during any study phase (i.e., run-in, treatment, washout, follow-up), that fulfils one or more of the following criteria:

- Results in death

- Is immediately life-threatening
- Requires in-subject hospitalisation or prolongation of existing hospitalisation
- Results in persistent or significant disability/incapacity or substantial disruption of the ability to conduct normal life functions
- Is a congenital abnormality or birth defect
- Is an important medical event that may jeopardise the subject or may require medical intervention to prevent one of the outcomes listed above.

For further guidance on the definition of a SAE, see [Appendix B](#) to the Clinical Study Protocol.

6.3 Recording of adverse events

6.3.1 Time period for collection of adverse events

All AEs, including SAEs, will be collected from the time the subject signs the informed consent throughout the treatment period and including the follow-up period.

6.3.2 Follow-up of unresolved adverse events

Any AEs that are unresolved at follow-up in the study will be followed up by the investigator for as long as medically indicated, but without further recording in the CRF. AstraZeneca retains the right to request additional information for any subject with ongoing AE(s)/SAE(s) at the end of the study, if judged necessary.

The requirement to follow-up AEs is not intended to delay database lock or production of the Clinical Study Report (CSR). These activities should proceed as planned with ongoing AEs if necessary.

Any follow-up information of ongoing SAEs after database lock will be reported to AstraZeneca.

6.3.3 Variables

The following variables will be collect for each AE;

- AE (verbatim)
- The date and when the AE started and stopped
- Maximum intensity of the AE
- Whether the AE is serious or not

- Investigator causality rating against the IP (yes or no)
- Action taken with regard to IP
- AE caused subject's withdrawal from study (yes or no)
- Outcome.

In addition, the following variables will be collected for SAEs:

- Date AE met criteria for serious AE
- Date Investigator became aware of serious AE
- AE is serious due to
- Date of hospitalisation
- Date of discharge
- Probable cause of death
- Date of death
- Autopsy performed
- Causality assessment in relation to Study procedure(s)
- Description of AE.

It is important to distinguish between serious and severe AEs. Severity is a measure of intensity whereas seriousness is defined by the criteria in Section 6.2. An AE of severe intensity need not necessarily be considered serious. For example, nausea that persists for several hours may be considered severe nausea, but not a SAE. On the other hand, a stroke that results in only a limited degree of disability may be considered a mild stroke but would be a SAE.

6.3.4 Causality collection

The Investigator will assess causal relationship between IP and each AE, and answer 'yes' or 'no' to the question 'Do you consider that there is a reasonable possibility that the event may have been caused by the investigational product?'

For SAEs causal relationship will also be assessed for other medication and study procedures. Note that for SAEs that could be associated with any study procedure the causal relationship is implied as 'yes'.

A guide to the interpretation of the causality question is found in [Appendix A](#) to the CSP.

6.3.5 Adverse events based on signs and symptoms

All AEs spontaneously reported by the subject or reported in response to the open question from the study personnel: *'Have you had any health problems since the previous visit/you were last asked?'*, or revealed by observation will be collected and recorded in the CRF. When collecting AEs, the recording of diagnoses is preferred (when possible) to recording a list of signs and symptoms. However, if a diagnosis is known and there are other signs or symptoms that are not generally part of the diagnosis, the diagnosis and each sign or symptom will be recorded separately.

6.3.6 Adverse events based on examinations and tests

The results from protocol mandated laboratory tests and vital signs will be summarised in the clinical study report. Deterioration as compared to baseline in protocol-mandated laboratory values and vital signs should therefore only be reported as AEs if they fulfil any of the SAE criteria or are the reason for discontinuation of treatment with the IP.

If deterioration in a laboratory value/vital sign is associated with clinical signs and symptoms, the sign or symptom will be reported as an AE and the associated laboratory result/vital sign will be considered as additional information. Wherever possible the reporting Investigator will use the clinical, rather than the laboratory term (e.g., anaemia versus low haemoglobin value). In the absence of clinical signs or symptoms, clinically relevant deteriorations in non-mandated parameters should be reported as AE(s).

Any new or aggravated clinically relevant abnormal medical finding at a physical examination as compared with the baseline assessment will be reported as an AE. Cases in which a patient shows an AST or ALT $\geq 3xULN$ or total bilirubin $\geq 2xULN$ may need to be reported as SAEs (please refer to Appendix C 'Actions required in cases of combined increase of Aminotransferase and Total Bilirubin – Hy's Law', for further instructions).

An adverse event will also include any untoward or unfavorable medical occurrence associated with the following study mandated procedures and/or occurring within 48 hours after:

- Allergy Skin Test
- Sputum Induction
- Bronchoscopy
- Whole Lung Allergen Challenge
- Methacholine Challenge
- Whole blood collection

- Bone Marrow Aspirate

The following clinical situations, when associated with study procedures will be considered to be outside of the normal range of findings and will be recorded as Adverse Events. These situations do not limit the principal investigator from reporting any other events, associated or not with these procedures, from being recorded and reported as AEs.

Blood Draws

- Fainting /Vasovagal events
- Bruising at puncture site larger than 2 cm diameter
- Bleeding from puncture site lasting more than 5 minutes
- Swelling at puncture site larger than 2 cm

Allergen Skin Testing

- Prolonged (>24 hours) itching at test site
- Swelling (> 10 cm) at site of test lasting more than 24 hours
- Nasal allergic symptoms within 30 minutes from the procedure
- Fainting /Vasovagal event within 30 minutes from the procedure
- Systemic reaction

Pulmonary Function Testing

- Wheezing or bronchoconstriction requiring treatment with bronchodilators within 30 minutes from the procedure
- Coughing requiring treatment with bronchodilators within 30 minutes from the procedure

Methacholine Challenge

- FEV₁ has not returned to at least 90% of the baseline (pre-diluent) value with 4 puffs of salbutamol
- FEV₁ drops by more than 50% during the procedure

Allergen Inhalation challenge

- Systemic Reaction

- Asthma exacerbation requiring prednisone therapy
 - Significant decrease in lung function
- a). FEV₁ decreases by >60% from baseline (defined at the highest pre-test FEV₁ on the day of the allergen challenge Visit)
- or
- b) FEV₁ decreases by 40-59% from baseline AND does not begin to recover spontaneously during the first 60 minutes post immediate decline in FEV₁, OR does not respond to salbutamol therapy employed to reverse bronchoconstriction
- or
- c) Failure to recover to within 80% of baseline FEV₁ at discharge. Salbutamol therapy may be used to assist in recovery.

Bronchoscopy

- Asthma exacerbation requiring prednisone in response to bronchoscopy
 - Significant decrease in lung function
- a) FEV₁ decreases by >60% from baseline
- or
- b) FEV₁ decreases by 40-59% from baseline AND does not begin to recover spontaneously during the first 60 minutes post immediate decline in FEV₁, OR does not respond to salbutamol therapy employed to reverse bronchoconstriction
- or
- c) Failure to recover to within 80% of baseline FEV₁ at discharge. Salbutamol therapy may be used to assist in recovery.
- Significant hypoxemia during bronchoscopy
 - The bronchoscopy procedure results in hypoxemia of <85% oxygen saturation for greater than 30 seconds despite supplemental O₂.

6.3.7 Symptoms of the disease under study

When collecting AEs, the recording of diagnoses is preferred (when possible) to recording a list of signs and symptoms. Asthma symptoms or signs, such as wheeze, cough, chest tightness, dyspnoea, breathlessness and phlegm, will be recorded as AEs only when:

The sign or symptom is serious according to definitions, see Section 6.2.

The patient discontinues the study due to the sign or symptom

The sign or symptom is new to the patient or not consistent with the patient's pre-existing asthma history (defined as within 1 year of Visit 1a) as judged by the investigator.

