3.9 Discontinuation of investigational product

Subjects will be discontinued from investigational product (IP) in the following situations:

- Subject decision. The subject is at any time free to discontinue treatment, without prejudice to further treatment (see Section 3.1)
- Adverse event (AE) that, in the opinion of the investigator, contraindicates further dosing
- Risk to subject as judged by the investigator or AstraZeneca
- Severe non-compliance to study protocol
- Eligibility requirement found not to be fulfilled (see section 3.4)
- Pregnancy
- Lost to follow-up¹
- IP unblinding

¹ Subject is considered lost to follow up when the following two attempts of contact are failed: 3 attempts of either phone calls, faxes or emails and having sent 1 registered letter/certified mail.

² Oral corticosteroids may be used to rescue after allergen challenge if needed. If the subject has to use inhaled or oral corticosteroids, the remaining secondary and exploratory outcomes of the allergen challenge triad should be aborted. Subjects will report for safety assessments, including spirometry.

- Development of any study specific criteria for discontinuation:
 - (a) Anaphylactic reaction to the investigational product requiring administration of epinephrine.
 - (b) Development of helminth parasitic infestations requiring hospitalization.
 - (c) If one dose of IP is missed during course of the study.
 - (d) An asthma-related event requiring an ER visits or use of oral corticosteroids²
 - (e) Worsening of asthma, as judged by the investigator

All subjects who prematurely discontinue IP should return to the study centre and complete the procedures described for the IPD (Premature IP Discontinuation) visit and Follow-up visit within 4 weeks (+7 days) and 12 weeks (± 7 days) after the last dose of IP, respectively.

Reasons for premature discontinuation of IP should be recorded in the eCRF.

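### The asthma AE rule in section 6.3.7 is triggered by leaving the study, not by stopping IP, and it is not reconciled with the post-procedure AE rules in section 6.3.6

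*Protocol*

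**What the plan says.** Section 6.3.7 sets a restrictive rule: "Asthma symptoms or signs, such as wheeze, cough, chest tightness, dyspnoea, breathlessness and phlegm, will be recorded as AEs only when" one of three conditions is met. These are that "The sign or symptom is serious according to definitions, see Section 6.2"; that "The patient discontinues the study due to the sign or symptom"; or that "The sign or symptom is new to the patient or not consistent with the" subject's asthma history, as judged by the investigator. The same section states that "the recording of diagnoses is preferred (when possible) to recording a list of signs and symptoms".

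Section 3.9 lists reasons for stopping IP. They include "An asthma-related event requiring an ER visits or use of oral corticosteroids" and, as a separate item, investigator-judged worsening of asthma. Subjects who stop IP early are asked to attend the IPD visit and the Follow-up visit.

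Section 6.3.6 adds a rule tied to procedures. An AE also includes "any untoward or unfavorable medical occurrence associated with the following study mandated procedures and/or occurring within 48 hours after" a list of procedures that contains allergen challenge, methacholine challenge and sputum induction. A second list then names situations regarded as beyond the normal range of findings, which are AEs. For the allergen challenge it includes "Asthma exacerbation requiring prednisone therapy" and large FEV1 falls. For lung function testing it includes wheeze or cough treated with a bronchodilator in the following 30 minutes. Section 6.3.6 says that this second list does not restrict what else the investigator may report.

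Section 8.5.3 plans summaries of AEs leading to discontinuation and, by name, AEs leading to study discontinuation.

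**The concern.** Two separate defects in the recording rules affect asthma events.

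The first is a mismatch between section 6.3.7 and section 3.9. Asthma is a stated reason to stop IP, and a subject who stops IP is still followed. The AE trigger in section 6.3.7 is leaving the study, which is a different event. An asthma symptom that ended treatment could thus be outside the AE data, although it bears directly on tolerability in an asthma trial.

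The second lies between section 6.3.6 and section 6.3.7. For ordinary asthma symptoms after a procedure, one section includes what the other leaves out, and neither says which applies. All subjects are selected for a dual response to allergen, so such symptoms should be expected at the challenge visits. With six centres, recording could depend on which section the site staff follow.

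**Working it through.** No figure in the protocol depends on this point, so the check is a comparison of text.

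**Step 1: does the protocol treat stopping IP and leaving the study as different?** Yes, in several places.
- Section 3.9 covers stopping IP, and section 3.10.2 covers withdrawal from the study.
- Section 6.3.3 collects the action taken with IP separately from whether the AE caused withdrawal from the study.
- The abbreviation list defines DAE by discontinuation of IP.
- Section 8.5.3 names discontinuation and study discontinuation separately.
- For laboratory values and vital signs, section 6.3.6 uses stopping IP as the trigger.

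The word study in section 6.3.7 therefore cannot be assumed to cover IP.

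**Step 2: apply the rules to concrete cases.** In cases A, D and E the symptom is non-serious, in line with the subject's asthma history and recorded without a diagnosis.

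| Case | Section 6.3.6 | Section 6.3.7 |
|---|---|---|
| A. Wheeze between dosing visits, not near a procedure; IP stopped as asthma worsening; subject attends IPD and Follow-up | No rule applies | Not an AE |
| B. As A, but recorded as the diagnosis of an exacerbation | No rule applies | Outside the restriction, which covers signs and symptoms; can be recorded |
| C. Bronchospasm needing intensive emergency-room treatment | No rule applies unless near a procedure | AE as serious, by the examples in Appendix A |
| D. Wheeze five hours after allergen challenge, FEV1 fall below the listed limits | AE if the 48-hour sentence is read alone; unclear if read with the list | Not an AE |
| E. Wheeze or cough treated with a bronchodilator within 30 minutes of lung function testing | AE | Not an AE |
| F. Exacerbation treated with prednisone after allergen challenge | AE | Diagnosis, so no conflict |

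Case A is the gap. Case E is a direct contradiction. Case D is a contradiction on one reading and an ambiguity on the other.

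**Step 3: how wide is the gap in case A?** It needs four things together: a non-serious symptom, a judgement that it fits the subject's history, no recorded diagnosis, and a subject who remains in the study. Such a judgement is possible, because inclusion criterion 6 requires a history of episodic wheeze and breathlessness. Appendix A also says that emergency-room treatment does not in itself make an event serious. In time, the gap is confined to the dosing period. Doses are given at Day 0, Week 4 and Week 8, and the post-treatment allergen challenges follow the third dose, so symptoms from those challenges cannot stop a later dose.

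**Step 4: size.** The planned total is about 38 subjects, so 38/2 = 19 per arm. One omitted event is 1/19 = 5.3% of an arm. This describes the arm size and does not estimate how many events would be lost. The protocol gives no rate of IP stops for asthma and no rate of post-challenge symptoms.

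**The case against.** The strongest reply is that most asthma events that matter are already captured. Section 6.1 counts deterioration of an existing condition as an AE. Sections 6.3.5 and 6.3.7 prefer diagnoses, and the asthma reasons in section 3.9 read as diagnosis-level events. Appendix A gives intensive emergency-room or home treatment of allergic bronchospasm as an example of an important medical event. Subjects enter with mild, stable asthma, so a worsening that stops IP will often be inconsistent with their history and meet the third condition. The reason for stopping IP is entered in the eCRF in any case. All of this stands and narrows the gap, but it does not close it, because each route depends on how the investigator labels or judges the event. An eCRF reason for stopping is also not an AE record, and section 8.5.3 summarises AEs.

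On the post-procedure rules, the reply is that a list of findings beyond the normal range implies that ordinary challenge responses are within it. That is a fair reading. It does not settle the matter, since the list is expressly open, and it does not help with case E, which is on the list itself.

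A reader might go further and infer that section 6.3.7 excludes every asthma sign that stops IP; that the induced late response is itself an AE in all placebo subjects at Visit 11, so that a drug effect on it would look like a safety advantage; or that asthma AE counts are unreliable in both directions. The documents do not support these. Serious, new and diagnosed events remain AEs. The contrast between everyone and no one is only the bound between two literal readings. Both blinded arms follow the same rules, and safety is summarised descriptively.

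**Conclusion.** The point holds in a limited form. As written, section 6.3.7 allows a non-serious, history-consistent asthma symptom without a recorded diagnosis to end dosing without becoming an AE, and so to be missing from the summary of AEs leading to discontinuation. This is a mismatch with section 3.9, and a different trigger from the one used for laboratory values and vital signs. It is not a conflict with the procedure rules. Separately, sections 6.3.6 and 6.3.7 give different answers for the same post-procedure asthma symptoms and state no precedence, so recording can differ between sites. The effect on AE counts cannot be sized from the protocol, and no bias between arms is shown. The conclusion assumes that sites apply section 6.3.7 as worded and that no eCRF instruction, which is not shown, already resolves the point.

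**What to change.** In section 6.3.7, amend the second condition so that it is met when the patient stops IP or leaves the study because of the sign or symptom. Add that an asthma event that is the reason for stopping IP under section 3.9 is recorded as an AE.

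Reconcile section 6.3.6 with section 6.3.7 by stating which AE-recording rule governs asthma symptoms and FEV1 falls after allergen challenge, methacholine challenge and lung function testing, including the bronchodilator-treated wheeze and cough items. Keep the investigator's freedom to report other events. Making the list of thresholds decisive would close a list that the protocol leaves open, and would narrow safety capture.

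These changes concern AE recording only; no dosing, stopping or rescue rule is altered. The cost is a few amendment sentences and eCRF completion guidance, and possibly slightly more AEs recorded.
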